# A) Mixed Meal Tolerance Test (MMTT) at Visit 1 or 2 (approx 2½ hours)

**Rationale:** The MMTT will provide confirmatory analysis of post-mixed meal glucagon stored in BD P800 and EDTA plasma samples at a range of standard MMTT time points (0, 30, 60, 90 and 120 min) in 75 people. Glucose will be measured in Fluoride Oxalate samples at the same time points.

# Participants will:

- be monitored closely throughout their visit for any discomfort or problems and appropriate advice/support will be given if required.
- be given Ensure HP or Fortisip (6ml/kg to a max of 360mls)
- have blood samples collected, to measure insulin, C-peptide, glucose, and glucagon, at specific intervals: -10, 0, 30, 60, 90, 120 minutes post meal

At the end of the MMTT procedure, the participant's blood glucose will be checked and appropriate advice will be given relating to insulin dosage adjustments prior to a light meal being provided.

17

Version 2.0 04/11/2022

IRAS: 319581

# B) Arginine Stimulation Test (AST) Visit 1 or 2 (approx 1 hour)

Rationale. An MMTT (despite being convenient because it avoids the need for an IV stimulus) has limitations, including differences in gastric emptying, uptake and effects on enteroendocrine secretion. Therefore, we will compare responses during the MMTT with those obtained during an intravenous arginine challenge, Arginine Stimulation Test (AST), (5 g Arginine during 1 min) at a separate visit from the MMTT visit. Glucose, plasma glucagon and C-peptide will be measured at baseline and specific intervals (see below) minutes following the Arginine bolus injection. This test is designed primarily to test the maximum insulin secretion capacity of a participant's beta cells.

#### The AST test involves:

- 1. Set up. Intravenous catheters will be inserted into antecubital veins in both arms. One arm will be used for infusion of Arginine (amino acid), and the other arm for intermittent sampling. Blood glucose concentration will be monitored with regular YSI measures throughout the test.
- 2. AlRarg (acute insulin response to arginine). Baseline samples will be taken at -10 and 0 minutes. A maximally stimulating dose of Arginine Hydrochloride (5 g) will be injected intravenously for 45s. Samples will be collected at 2, 5, 10, 15 and 30 minute intervals following the Arginine bolus.
- 3. At the end of the AST procedure, the participant's blood glucose will be checked and appropriate advice will be given relating to insulin dosage adjustments prior to a light meal being provided.

# C) 'Light MMTT' – Visit 3, approx 6 months after Visit 1 (2 hours)

The participants will be invited to the research facility approximately 6 months after their first visit to undergo a 'Light MMTT'. This test is as described above for MMTT but we will only collect a single sample at the most informative time, as assessed from the first MMTT and AST. We will repeat clinical data collection, hypoglycaemia questionnaires, 2-week CGM data collection with participant blinded *Abbott FreeStyle Libre Pro*.

**At Visit 3**, the choice of test will be either a 'Light MMTT' or a repeat AST and will be determined by the peak glucagon results from the tests conducted at Visits 1 and 2.

## 4.4 Data Collection and Recording

All participants will be assigned a unique study ID. All data and samples collected will be recorded and stored under this ID number. Data will be initially recorded using a study-specific case report form (CRF), with hard copies stored in the Trial Master File (TMF). Anonymised research data will be recorded on a study-specific database. Exeter CRF data quality procedures require data collected and recorded to be screened and reviewed for discrepancies and missing data prior to analysis.

Baseline data to be collected will include:

- Personal identifiers
- Physical measures, including BMI
- Diabetes & other significant medical history
- Medication history
- Blood biochemistry

Permission will be obtained to access medical notes should this be required for diabetes data relevant to taking part in the project.

### 4.5 End of Study Definition

The parameter marking the end of the study is the 3 months after the final participant's 7 months follow-up period to allow for final collection of data.

### 4.6 Subject Withdrawal

Subjects will be informed they are free to withdraw from the study at any time up to and including data and sample analysis, without prejudice or jeopardy to any future clinical care. If a patient permanently withdraws from the study, or is lost to follow up, the reason will be recorded.

Criteria for premature withdrawal from the study:

Participant withdrawal of consent

- Investigators' discretion that it is in the best interest of the participant to withdraw
- Termination of the study by the trial sponsor.

# 4.7 Data Collection and Follow-up for Withdrawn Subjects

Where a participant withdraws, data will be collected up to the point of withdrawal in line with the protocol and study SOPs. If appropriate, the PI or delegated member of the research team will follow-up with the participant to ensure wellbeing and that ongoing clinical care is unaffected.

Where a participant has prematurely withdrawn but not revoked consent, data and samples will remain within the study and included in any analysis. Where consent is withdrawn, study samples and data will be kept/destroyed as per the following options in line with data SOPs and local guidelines:

- samples and data remain
- samples withdrawn, data remains
- samples remain, data withdrawn
- both samples and data withdrawn.

Withdrawal will be recorded on the study database and the participant's choice of the above options recorded. A withdrawn participant is not obliged to give a reason for withdrawing their consent but, where they are willing to do so, the reason will be documented. Details of all withdrawn participants will be regularly reviewed to enable any study-wide trends relating to study procedures to be ascertained and acted upon where appropriate.

# 5. Samples

### 5.1 Sample Collection / Labelling / Logging

All samples will be collected by a suitably qualified and trained member of the research team, whose role is documented on the study delegation log. A detailed SOP/work instruction will be provided detailing the clinical procedure for collecting samples and the logistics of sample labelling, logging and management. All study-specific procedures will be covered during the Site Initiation Visit.

### 5.2 Laboratory Assessments and Results Reporting

The Exeter Clinical Laboratories have an established pipeline for receiving and processing all research samples, including documentation of chain of custody. Central laboratory analysis of the study samples will be undertaken at the Exeter Blood Sciences Laboratory at the Royal Devon University Healthcare NHS Foundation Trust site. Upon receipt, the specimens will be assessed for content and integrity. The samples will be logged immediately, and all samples will be tracked using the laboratory information management system (LIMS).

All analyses are routine biochemistry tests available in the NHS test repertoire. All assays are CE marked, fully validated and accredited by CPA (Clinical Pathology Accreditation).

The Exeter Blood Sciences Laboratory will provide the Site PI with the results of HbA1c, C-peptide, and glucose within 21 days of receipt of the sample. Results of tests analysed in Exeter will also be uploaded directly to the study database within 21 working days of consent date. Surplus plasma and serum will be stored pending consent and will be destroyed if consent is not given within 3 months of sample receipt. Stored plasma, serum, fluoride oxalate, PAXgeneRNA, and P800 will be used for batched analysis of biomarkers such as glucagon, proinsulin, glucose, RNA, and other factors associated with T1D (e.g. immune system).

#### 5.3 Stored samples

Surplus samples for storage should be processed, logged and frozen at -80°C within 24 hours of receipt. All saved samples will be stored under the study ID, with the file linking the study code to personal identifiable information held securely by the Principal Investigator, accessible only to personnel with training in data protection who require this information to perform their duties. Those with access to personal identifiable data will be documented on the study Delegation Log.

Version 2.0 04/11/2022

IRAS: 319581 19

All samples sent to the Exeter Clinical Laboratories must be logged on the study sample database. The Study ID and barcode set will provide a robust pseudo-anonymised system for management of all samples. The research team will monitor consent status via the study database. Samples without consent to store will be destroyed within 3 months of collection. Where samples are unable to be collected, this should be documented under the participant Study ID with reason for non-collection provided. At the end of the study, samples without consent to gift to the Peninsula Research Bank (PRB) will be destroyed.

# 6. Safety, Definitions and Reporting

#### 6.1 Risks

The blood samples will be collected by members of the research team trained in venepuncture. Any potential discomfort or side-effects will be equivalent to that experienced in routine clinical care. During the MMTT/AST test, there is a risk of hyperglycaemia (from having a meal without the participants' usual mealtime insulin) but risks will be minimized by participants being closely monitored during and after their visit by the diabetes specialist research team. Appropriate advice/support will be given if required.

#### 6.2 Benefits

In the short term, we hope to gain an improved understanding of participants' hypoglycaemia risk. In the longer term, this work may provide evidence that the ability of alpha cells to release glucagon after a mixed meal is variable within people with T1D, associated with hypoglycaemia risk, and could be a biomarker for hypoglycaemia risk.

## 6.3 Definitions and reporting of adverse effects (what should be reported?)

The timeframe for recording SAEs will be from the time of consent to one week following the last visit of a study subject. Any reportable adverse effects noted will be reported within 24 hours to the CI and the Sponsor as per standard NHS R&D protocols. Nominated co-investigators will be authorised to sign the SAE forms in the absence of the CI at the co-ordinating site, or the PI at the participating sites. *The Sponsor should be informed of these nominated individuals*.

### 6.4 Serious Adverse Event (SAE)

An SAE fulfils at least one of the following criteria:

- Is fatal results in death (NOTE: death is an outcome, not an event)
- Is life-threatening
- Requires inpatient hospitalisation or prolongation of existing hospitalisation
- Results in persistent or significant disability/incapacity
- Is a congenital anomaly/birth defect.

### Reportable SAEs

ANY hospitalisation relating to diabetes management, including DKA and serious hypoglycaemia.

**All reportable SAEs** will be recorded in the subject's medical notes, the local Investigator Site File, and the Sponsor SAE form and reported to the Sponsor and CI/central coordinating team, within 24 hours of the CI or PI or co-investigators becoming aware of the event.

**All non-reportable SAEs** will be recorded in the subject's notes, and the CRF, but the Sponsor SAE form will not be filled out or reported to the Sponsor and Cl/central coordinating team.

The following SAEs will be considered recordable but **not reportable** to the Sponsor:

- Hospitalisation for elective treatment
- Hospitalisation for treatment of a pre-existing condition
- Hospitalisation for non-diabetes related reasons
- Hospitalisation due to road traffic accident

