# Tests and blood samples:

Visits 1 and 2 will be approximately 3-7 days apart. The order of test will be randomised to check for a test order effect. Visit 3 will be approximately 6 months after Visit 1 and the test conducted will be determined by the peak glucagon results from Visits 1 and 2.

A small cannula (thin plastic tube) will be inserted into a vein, following standard clinical practice, for the duration of each visit to facilitate repeat sampling with minimal invasion, discomfort and potential trauma from repeat blood sampling. For the arginine stimulation test (AST), a cannula will also be inserted into a vein in the non-sampling arm to administer the arginine bolus.

Fasted samples will be obtained for baseline measures: routine glucose and HbA1c, plasma and serum for storage and future batched analysis including measures of glucose, glucagon, insulin (C-peptide) and other markers of interest, plus sodium heparin and PAXgenesRNA samples for T1D immune function analysis.

Stimulated samples (see test descriptions below): insulin (C-peptide), glucose and glucagon will be measured at all time points.

Spare aliquots from all time points will be saved and stored at -80°C for batched analysis of other biomarkers if required.

The exact number of blood samples may vary but the total amount of blood we will collect at each visit will not exceed 150 millilitres (ml).

At the end of each test period, the participant's blood glucose will be checked and appropriate advice will be given relating to insulin dosage adjustments. The cannula(s) will be removed prior to a light meal being provided.

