### **7.2 Case Report Form** (data collection form)

The relevant visit Case Report Form (CRF) will capture all the information required to ensure that all the documented statistical information thus dictated in the protocol is captured and documented at each visit. This also serves to monitor patient eligibility and safety at Sponsor level.

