### 13. Quality Control and Quality Assurance

#### 13.1 Monitoring

Monitoring of this study will ensure compliance with Good Clinical Practice. The Investigator(s) will permit monitoring, audits, REC review, and regulatory inspections by providing the Sponsor(s), Regulators and REC direct access to source data and other documents (e.g. participants' case report forms, consent forms etc). Periodic remote monitoring will be carried out by the CI's study team and the Sponsor. Consent will be taken to permit access to data by external staff responsible for monitoring and auditing the study as a requirement of participating in the study. Remote monitoring of recruitment activities will be carried out periodically by the study management team (on behalf of the CI & Sponsor) by exploring data, consent forms, delegation log & recruitment log in accordance with the study SOPs/work instructions.

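### The SAE rule makes non-diabetes hospitalisations non-reportable to the Sponsor, with no exception for one possibly caused by a study procedure

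*Protocol*

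**What the plan says.** Protocol section 6.4 first defines an SAE by seriousness: death, threat to life, hospitalisation, disability or congenital anomaly. Under its sub-heading Reportable SAEs it then divides SAEs in two.

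- **Reportable.** One class is named: "ANY hospitalisation relating to diabetes management, including DKA and serious hypoglycaemia". These go to the Sponsor and to the chief investigator's central team within 24 hours of the investigators becoming aware.
- **Recordable but not reportable.** Four classes are named: elective treatment, treatment of a pre-existing condition, road traffic accident, and "Hospitalisation for non-diabetes related reasons". Non-reportable SAEs "will be recorded in the subject's notes, and the CRF, but the Sponsor SAE form will" not be completed, and no report goes to the Sponsor or the central team.

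Section 6.3 sets the same clock: "Any reportable adverse effects noted will be reported within 24 hours to the CI and the Sponsor". It collects SAEs from consent until one week after the last visit.

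The study carries out its own invasive procedures. For the arginine stimulation test, section 4.3 states: "A maximally stimulating dose of Arginine Hydrochloride (5 g) will be injected intravenously for 45s". A sampling cannula is placed at every visit, and for the arginine test "a cannula will also be inserted into a vein in the non-sampling arm to administer the arginine bolus". Participants are also offered a two-week CGM sensor.

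**The concern.** The study is observational, but participants undergo an injection, cannulations and sensor fitting because they are in the research. Complications of those procedures need not have anything to do with diabetes. A reporting rule that asks only whether the admission was for diabetes picks up the harms expected from fasting and from the meal. It passes over the others, however closely they followed a study procedure.

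What is at stake is timeliness. If an admission may have been caused by a procedure, the Sponsor needs to know while others are still due to have the same procedure. Recruitment is planned to run for 15 months, Visits 1 and 2 are about 3 to 7 days apart, and the arginine test may be repeated at Visit 3. No endpoint, estimate or analysis is affected; this is a participant-safety point.

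**Working it through.** No arithmetic applies: the protocol states no event rate and no figure is in dispute. The check is to apply the rule as written to plain cases, then look for any other text that would change the outcome.

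**Step 1: apply section 6.4.** The cases are hypothetical and say nothing about how often such events occur.

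| Case | Diabetes management? | Class in 6.4 | Sponsor form and 24-hour report? |
|---|---|---|---|
| Admission with ketoacidosis after the mixed meal test | Yes | Reportable | Yes |
| Admission for a reaction to the injected arginine | No | Non-diabetes reasons | No |
| Admission for infection or thrombophlebitis at a cannula site | No | Non-diabetes reasons | No |
| Death or life-threatening event without hospitalisation | Not asked | In neither list | Not stated |

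The second and third cases are SAEs, and they can fall inside the section 6.3 collection window. The text excludes them by express instruction. The fourth is a separate gap: the event is unassigned, not excluded.

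**Step 2: look for a relatedness exception elsewhere.**

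- Section 6.3: the 24-hour duty, and its reference to usual NHS R&D procedure, attaches only to effects that are already reportable. Section 6.4 decides which those are.
- Glossary: adverse reaction, serious adverse reaction and SUSAR are spelled out, but no operative rule uses them. No section requires a causality judgement.
- Section 13.3: serious-breach notification concerns breaches of GCP or of the protocol. A reaction to a correctly performed procedure is neither.
- Section 11: a general commitment to GCP, regulation and Trust policy, with no SAE rule of its own.

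**Step 3: list the remaining routes to the Sponsor and their timing.**

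| Route | Where | Time limit |
|---|---|---|
| CRF ("This also serves to monitor patient eligibility and safety at Sponsor level") | 7.2 | None stated |
| Monitoring ("Periodic remote monitoring will be carried out by the CI's study team and the Sponsor") | 13.1 | Periodic, interval not stated |
| Steering committee, with a Sponsor Representative | Study Steering Committee | Every 6 months; no SAE input specified |
| Review of withdrawn participants for trends linked to procedures | 4.7 | Regular, interval not stated; applies only if the participant withdraws |

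**Result.** An admission that a study procedure may have caused, but that is not diabetes-related, loses the Sponsor form and the 24-hour clock. No other route replaces that clock.

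**The case against.** The strongest case against has four parts.

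1. **The Sponsor has other ways to find out.** This is true, and they are listed above. A reader might infer that such an event would stay hidden from the Sponsor, or reach it only through the CRF or a monitoring visit. The documents do not support that: the steering committee and the withdrawal review are further routes. What stands is that none of them is prompt.
2. **At a single site, the people who matter already know.** Section 2.6 makes this a single-site study, and the chief investigator and project manager run it day to day. Participants are closely monitored during visits, with medical cover on site. Local staff would probably see an acute reaction, and the investigator can withdraw the participant. Losing the report to the central team is therefore largely nominal. What remains is the Sponsor's prompt, documented notice. A delayed complication after the participant has gone home is also less certain to be seen at once.
3. **Outside policies may require the report anyway.** Section 11 binds the study to GCP and to Trust and R&D policies that are not available here, and these may have their own rule. The claim must therefore be confined to the protocol text. Even so, that text tells staff not to complete the form, and any stricter policy would conflict with it.
4. **The procedures are ordinary.** Sections 6.1 and 12.1 describe blood sampling and cannulation as carrying only minor discomfort. A reader might infer from this finding that the arginine bolus or the cannulas are hazardous, or might multiply procedures by participants to suggest a number of harms. The documents give no event rate, so neither inference is available. The argument does not need one: a reporting rule exists for the uncommon event.

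**Conclusion.** The concern holds as a gap in the protocol's reporting rule. Section 6.4 sorts by reason for admission and never asks about relatedness, so a non-diabetes hospitalisation possibly caused by the arginine injection, a cannula or the sensor is expressly kept out of 24-hour Sponsor reporting. The size is one class of event losing one form and one clock. The likely number of such events cannot be stated from the documents.

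Two stronger readings should be resisted. It would be wrong to say that the protocol excludes deaths and life-threatening events from reporting: without a hospitalisation they are in neither list, which needs tidying but is not an instruction to withhold. It would also be wrong to treat all four non-reportable classes as equally at fault; the non-diabetes class carries the problem.

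The conclusion assumes that staff follow section 6.4 as written and that no policy outside the protocol overrides it. A missing statistical analysis plan does not explain the gap, because SAE reporting is a protocol matter. The change should be made: it is small and improves participant safety.

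**What to change.** Amend section 6.4 as follows.

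- Add to the reportable list, within the existing 24 hours, any SAE judged possibly related to a study procedure: fast, mixed meal, arginine bolus, cannulation or CGM sensor.
- Qualify the non-reportable list with the words *unless possibly related to a study procedure*.
- Have the investigator record relatedness on the CRF for every SAE when it is first recorded, before it is classed as reportable or not. The order matters: a non-reportable SAE has no Sponsor form, so a judgement made only on that form would never be made for the events at issue.
- Assign deaths and life-threatening events to the reportable list.

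The cost is amendment wording, one CRF field and one judgement per SAE, with possibly a few more Sponsor SAE forms. No visits, samples or analyses are added.

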#### 6.5 Pregnancy

If a patient becomes pregnant whilst involved in this study, it is not considered to be an SAE or an AE. If a patient becomes pregnant, this must be recorded on the CRF, including details of gestation and outcome.

#### 6.6 Insurance

Sponsor's public liability will be provided by the University of Exeter for the design and management of the study. NHS indemnity will apply for the conduct of the study at the site.

